3.4 Rationale for choice of comparator

This study does not include a placebo arm. Efficacy in terms of signs and symptoms is well established for secukinumab 150 mg for patients with active AS. Moreover, a placebo cohort would not be deemed ethically justifiable for this 1-year study, considering AS is known to be a chronic progressive disease with structural damage.

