### **2.2.1 Subgroup of interest**

Subgroup analyses will be performed for all the efficacy variables based on the TNF-alpha inhibitor status (naive, inadequate responder).

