### 5.4 Statistical models

#### 5.4.1 Primary analysis

The primary analysis will be performed comparing treatments with respect to the primary efficacy variable in a logistic regression model with treatment, TNF-alpha inhibitor (naive, inadequate responder) and baseline body weight as explanatory variables.

```
Proc logistic data=aaa;  
Class TRT TNF/ param=glm;  
Model AVAL= TRT TNF base_weight;  
Lsmeans TRT / diff cl exp;  
Ods output diffs=lsd_diff;  
Run;
```

Where TRT = treatment group  
TNF = TNF-alpha inhibitor (naive, inadequate responder)  
Base\_weight = baseline body weight

Logistic regression will be applied to response variables at each visit.

In cases where separation is a concern, e.g., 0% response in one treatment group, an exact logistic regression model will be applied.

```
Proc logistic data=aaa exactly;  
Class TRT TNF / param=glm;  
Model AVAL = TRT TNF base_weight;  
Exact TRT / estimate;  
Ods output exactoddsratio=exactoddsratio;  
Run;
```

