    lsmeans trt_ / diff;
    estimate 'AIN457 150 mg vs AIN457 300 mg' trt_ 1 -1;
    estimate 'AIN457 150mg mg vs Placebo' trt_ 0 1 -1;
    ods output Estimates=imp_est;

run;

proc mianalyze data=imp_est;
    by avisitn trt_ ;
    modeleffects LBetaEstimate;
    stderr StdErr;
    ods output ParameterEstimates=_res;

run;
```

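### The exact logistic fallback for separation conditions on body weight, so with one responder (or two in a small TNF-IR subgroup) it usually or often yields no treatment odds ratio

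*SAP*

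**What the plan says.** - **Rule.** SAP 5.4.1 gives the fallback for sparse cells: "In cases where separation is a concern, e.g., 0% response in one treatment group, an exact logistic regression model will be applied". No further step is given if the exact model itself yields no estimate.
- **Model.** The main program's model line, "Model AVAL= TRT TNF base_weight", is repeated in the exact program. The exact request is "Exact TRT / estimate", so TNF status and weight are conditioned out. The output line is "Ods output exactoddsratio=exactoddsratio".
- **Promised output.** SAP 2.5.2 and 2.7.2 promise odds ratios with 95% confidence intervals for the primary and the binary secondary variables.
- **Where it runs.** SAP 5.4.1 applies the model at each visit, and SAP 5.4.3 extends it to the binary secondaries. SAP 2.2.1 adds: "Subgroup analyses will be performed for all the efficacy variables based on the TNF-alpha inhibitor status".
- **MI odds-ratio program (also SAP 5.4.1).** It reads a data set named `acr20_mi`. It contains the line "estimate 'AIN457 150mg mg vs Placebo' trt_ 0 1 -1", whereas Protocol 3.4 says: "This study does not include a placebo arm". It then pools by visit and `trt_`.

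**The concern.** Exact logistic regression removes nuisance parameters by conditioning on their sufficient statistics. For body weight, that statistic is the sum of the responders' weights. Weight is close to continuous, so when there are very few responders there may be no other set of patients with the same sum and TNF count but a different treatment split. The conditional distribution of the treatment count is then a single point. The likelihood is flat in the treatment effect, and there is no odds ratio, no confidence interval and no informative p-value.

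The fallback is meant for cells where ordinary logistic regression breaks down. If it breaks down in the sparsest of those cells too, the table has a gap where the SAP promises an odds ratio, and the analyst must choose a substitute after seeing the data.

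**Working it through.** **Inputs from the documents.** 97 patients per arm; Week 52 response 10% (150 mg) and 20% (300 mg); half-width 10% for a two-sided 95% interval (SAP 3). TNF-IR patients are at most 40% of those enrolled (SAP 1.1). If that mix carries through to randomization, 0.40 × 194 = 77.6, or about 39 per arm.

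**Assumptions, not in the documents.** Weight mean 88 kg, SD 20 (15 and 25 also tried in the FAS); recorded to 1, 0.1 or 0.01 kg; FAS 60% TNF-naive; a smaller TNF-IR subgroup of 20 per arm; response rates other than 10% and 20%. Protocol 6.6.6 describes how weight is measured but not its precision.

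**1. The plan's own figures reproduce.** n = 1.96² × (0.2×0.8 + 0.1×0.9) / 0.10² = 96.04, rounded up to 97. At 97 the half-width is 1.96 × √(0.25/97) = 9.95%. Odds ratio = (0.2/0.8)/(0.1/0.9) = 2.25. 270 × 0.9 × 0.8 = 194.4.

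**2. One responder, by hand.** The distribution has more than one point only if someone in the other arm, in the same TNF stratum, has the same recorded weight. For Normal weights with SD 20, two patients share a 0.1 kg value with probability about 0.1/(2 × 20 × √π) = 0.0014. With m candidates, the chance of no match is about exp(−0.0014m): 0.95 for m = 39 and 0.97 for m = 20. In the FAS (m = 58 or 39) it is 0.92 to 0.95.

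**3. Enumeration.** With all responders in one arm, every set with the same total, TNF count and weight sum was counted, over 100–400 simulated trials per cell. Percentage with no odds ratio (ranges are across repeated runs):

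| Per arm | Weight recorded to | 1 responder | 2 | 3 |
|---|---|---|---|---|
| 97 (FAS) | 1 kg | 50 | 0–1 | 0 |
| | 0.1 kg | 92–95 | 4–5 | 0 |
| | 0.01 kg | 98 | about 60 | 0 |
| 39 (TNF-IR) | 1 kg | 58 | 0 | 0 |
| | 0.1 kg | 92–95 | 16–18 | 0 |
| | 0.01 kg | 100 | 82 | 5 |
| 20 (TNF-IR) | 1 kg | 75 | 4 | 0 |
| | 0.1 kg | 97 | 53–59 | 2–4 |
| | 0.01 kg | 100 | 93 | 48 |

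At SD 15 or 25, the FAS figures at 0.1 kg are 89–90%, 5–6% and 0%.

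**4. Failure once triggered.** Weighting by binomial probabilities, given none in one arm and at least one in the other, at 0.1 kg:

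| True rate in other arm | 1% | 2% | 5% | 10% | 20% |
|---|---|---|---|---|---|
| 97 per arm | 58% | 32% | 4% | 0% | 0% |
| 39 per arm | 80% | 67% | 36% | 9% | 0.3% |
| 20 per arm | 93% | 89% | 75% | 50% | 15% |

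**5. Trigger and failure together.**
- Planned rates, FAS: P(0 of 97 on 150 mg) = 0.9^97 = 0.000036. The fallback is effectively never used.
- Planned rates, 39 per arm: 0.9^39 = 0.016; times 0.003 = 0.005%.
- Planned rates, 20 per arm: 0.9^20 × (1 − 0.8^20) = 0.122 × 0.988 = 0.120; times 0.049, 0.147 or 0.286 (1, 0.1, 0.01 kg) = 0.6%, 1.8% or 3.4%.
- Half the planned rates (5% and 10%), 39 per arm: 0.95^39 × (1 − 0.9^39) = 0.135 × 0.984 = 0.133; times 0.044, 0.094 or 0.209 = 0.6%, 1.3% or 2.8%.
- Half the planned rates, 20 per arm: 0.95^20 × (1 − 0.9^20) = 0.358 × 0.878 = 0.315; times 0.244, 0.499 or 0.712 = 7.7%, 15.7% or 22.4%.

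**6. Alternatives at 97 per arm, none in one arm and 1, 2, 3 or 5 in the other.**
- Exact model on TNF status only: estimable in every case run. Median-unbiased odds ratio (lower 95% limit): 1.00 (0.03), 2.44 (0.19), 3.88 (0.41), 6.98 (0.94).
- Firth with weight kept: converged in all 200 runs at each count; median odds ratios 3.0, 5.1, 7.1, 11.5.

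**7. Code, by reading only (not run in SAS).** ESTIMATE without the odds keyword gives parameter estimates, so the odds-ratio table named in the output line is not created. In the MI program the data set name belongs to another endpoint, and a three-coefficient placebo contrast has no counterpart among two randomized groups. GENMOD's estimates carry visit, imputation and contrast label but not `trt_`, so pooling by `trt_` cannot run. Nothing exponentiates the pooled log odds ratio.

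**The case against.** The strongest reply is that the exposure is narrow.

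- **Few responders.** A reader might infer that the exact model fails whenever there are one to three responders. The enumeration does not support that. At 0.1 kg, three responders almost never fail, and two fail in only about 5% of FAS cases. Recording to 1 kg lowers every figure.
- **The primary result.** A reader might infer that the primary result is at risk. At the planned Week 52 rates the FAS trigger has probability 0.000036, and even at 39 TNF-IR patients per arm the joint chance is negligible. The 20-per-arm and 5% scenarios are illustrations.
- **No dose comparison at all.** This does not follow either. SAP 2.5.4 and 2.7.2 give a 95% interval for the difference in proportions in the FAS at each Treatment Period 2 visit, which is closer to the stated objective than an odds ratio. Subgroup cells keep counts and percentages, but no such interval is specified for them.
- **A mistyped option.** The line "Proc logistic data=aaa exactly" looks like an error for an exact-only option. It may equally be a PDF-reading error, and nothing here depends on it.
- **Little is recovered.** With one responder the weight-free exact odds ratio is 1.00 with lower limit 0.03. An unadjusted Firth fit of 0/39 against 3/39 gives 7.6 (0.70 to 1032). These intervals are wide, but they show the uncertainty and are fixed in advance.
- **The MI program.** It serves an additional analysis whose prose is clear, and the faulty pooling would stop the run rather than give a wrong number.

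All of this limits the size. It does not answer why the fallback conditions on weight, or what is reported when it returns nothing.

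**Conclusion.** The point stands in a limited form. The fallback usually gives no odds ratio or interval with one responder opposite an empty arm, and often gives none with two responders in a small TNF-IR subgroup. Beyond that, failure is uncommon unless the subgroup is very small and weight very finely recorded. The size depends on weight precision, subgroup size and subgroup response rates, none of which the documents give. The cells exposed are low-response visits and the TNF-IR subgroup. The Week 52 FAS primary analysis is untouched at the planned rates. The correction is worth making because the method is least reliable in the sparsest cells it was added for. The mismatch between the exact request and its output table, and the leftover MI code, are secondary.

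**What to change.** 1. **Fallback.** In SAP 5.4.1, remove body weight from the exact model, condition on TNF status only, and request odds ratios so that the output table exists. Alternatively, use Firth penalised logistic regression with the main model's covariates and a profile-likelihood 95% interval. State which is chosen.
2. **Weight variable.** If weight is kept, use the main model's variable. SAP 2.5.2 names Week 16 weight; SAP 5.4.1 and Protocol 9.4.2 name baseline weight. SAP 2.1.1 treats Week 16 as baseline for Treatment Period 2, so the two SAP wordings may mean the same thing, but the text should say so.
3. **MI odds-ratio program.** Read the imputed ASDAS inactive-disease data, delete the placebo contrast, pool by visit and contrast label, and exponentiate the pooled log odds ratio and its limits.

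The cost is a sentence of SAP text and a few lines of code. The exact option gives up weight adjustment in those cells; the Firth option shrinks the estimate slightly toward no effect.

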#### Multiple Imputation for Primary Efficacy Variable (ASDAS inactive disease response)

A linear regression model will be used to perform multiple imputation (MI) under a missing at random (MAR) assumption. To help preserve the relationship between outcome and covariates within each treatment, a separate model will be run for each treatment. This will also help ensure that the imputation model does not make stronger assumptions on data relations than the analysis model.

To ensure that results can be replicated, the data should be sorted by treatment group, TNF-alpha inhibitor status (naive, inadequate responder), and unique subject ID before running the model. The data should be in horizontal format with one subject per dataset row and should only include one component of the composite variable. Only dataset rows with a non-missing baseline assessment and at least one non-missing post-baseline assessment will be included.

Impute the missing values 500 times (NIMPUTE) with a seed=45706 as shown below:

```
proc mi data=min max=out=imp minmaxiter=10000000 nimpute=500 seed=45706;
    by trt TNF;
    var weight_Week16 var1_Week16 var1_week20-var1_week52;
    mcmc chain=multiple initial=em;
run;
```

Depending on the component to be imputed, the list of visits in the VAR statement will be adjusted. It will only contain visits where the respective component was planned to be assessed.

<min of scale> and <max of scale> refer to minimum and maximum imputed values and depends on the component:

- All scores measured on NRS: minval=0, maxval=10;
- hs-CRP: minval=0, maxval= (no maximum value)

The imputation of hs-CRP will be based on  $\log(\text{value}+1)$ .

If issues with convergence arise:

1. Change Markov Chain Monte Carlo (MCMC) to Fully Conditional Specification (FCS), and check whether it is converged;
2. If both MCMC and FCS do not converge, TNF-alpha inhibitor status should be removed from PROC MI.

This procedure should be repeated separately for each component of the composite variable.

The score as well as ASDAS response can now be calculated based on the complete data. The response rate will be calculated for each imputation and then combined using Rubin's rules.

In order to calculate the response rate for each imputation, PROC FREQ will be used as follows.

Calculate binomial proportion and standard error for each imputation.

```
proc freq data=<ASDAS>;
    by treat visit _imputation_ ;
    tables <response> / binomial (level=2 cl=wilson correct) ;
    ods output BinomialProp=imp_bpr;
run;
```

Transpose the dataset for subsequent use with PROC MIANALYZE.

```
proc transpose data=imp_bpr out=imp_trs(drop=_name_);  
  by treat visit _imputation_ ;  
  var nvalue1; id name1; idlabel label1;  
run;
```

Apply LOGIT transformation:  $y = \log(p/(1-p))$  and std. err. transformation:  $\langle \text{new se} \rangle = \text{se}/(p*(1-p))$

```
data logit;  
  set imp_trs(rename=( _bin_ =p e_bin=se));  
  by treat visit _imputation_ ;  
  lmean=log(p/(1-p));  
  lse=se/(p*(1-p));  
run;
```

The transformed binomial proportion estimates and standard errors are combined by applying Rubin's rules for multiple imputed data sets.

```
proc mianalyze data=logit;  
  by treat visit ;  
  modeleffects lmean;  
  stderr lse;  
  ods output ParameterEstimates=logitres;  
run;
```

The combined data should be transformed back using the following formula:  $p = 1/(1 + \exp(-y))$

```
data miexpres;  
  set logitres;  
  by treat visit ;  
  resti = 1/(1+exp(-estimate));  
  rlow = 1/(1+exp(-lclmean));  
  rupp = 1/(1+exp(-uclmean));  
run;
```

If all responses are imputed the same as 0 (or 1) for all imputation datasets for a specific treatment or subgroup, then the between-imputation-variation will be zero. The combined final response rate for the specific treatment would be presented as seen in any of the imputed datasets together with 95% confidence interval from Wilson's method (as obtained from PROC FREQ).

The following steps will be performed to handle special cases:

- If after imputation all responses (observed + imputed) are the same either 0 or 1 for all imputation datasets for a specific treatment, it will not be possible to perform a logit transformation and the response rate (0% or 100%) for these cases will be presented together with the 95% CI from Wilson's method (as obtained from PROC FREQ).
- If after imputation the average response rate is the same across all imputed datasets (but not 0 or 1), there is no between-dataset variation and Rubin's rules cannot be applied. Instead the average response will be used with 95% CI from Wilson's method (as obtained from PROC FREQ).

The odds ratio will be derived using GENMOD for each imputation, then combined using Rubin's rules again.

```
proc genmod data = acr20_mi descending;
    by avisitn _imputation_ ;
    class trt_ TNFRESN ;
    model aval = trt_ TNFRESN weight / link=logit dist=bin;
    lsmeans trt_ / diff;
    estimate 'AIN457 150 mg vs AIN457 300 mg' trt_ 1 -1;
    estimate 'AIN457 150mg mg vs Placebo' trt_ 0 1 -1;
    ods output Estimates=imp_est;

run;

proc mianalyze data=imp_est;
    by avisitn trt_ ;
    modeleffects LBetaEstimate;
    stderr StdErr;
    ods output ParameterEstimates=_res;

run;
```

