### **2.5.3 Handling of missing values/censoring/discontinuations**

Patients who discontinue prematurely for any reason will be considered nonresponders from the time they discontinued through Week 52. Also, patients who do not have the required data to compute response (ASDAS components) at the specific time point will be classified as nonresponders.

In an additional analysis, missing data for ASDAS inactive disease response will be imputed using multiple imputation. Details for multiple imputation is presented in Appendix [Section 5.4](#).

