### 2.11.1 ASDAS and ASDAS response categories

The Ankylosing Spondylitis Disease Activity Score (ASDAS) is a composite index to assess disease activity in AS. The ASDAS-CRP (Ankylosing Spondylitis Disease Activity Score) will be utilized to assess the disease activity status. Parameters used for the ASDAS calculation include spinal pain (BASDAI question 2), the patient's global assessment of disease activity, peripheral pain/swelling (BASDAI question 3), duration of morning stiffness (BASDAI question 6) and C-reactive protein (CRP) in mg/L ([Sieper 2009](#), [Lukas 2009](#)).

ASDAS-CRP is calculated in the following way:

$$\text{ASDAS-CRP} = 0.12 * \text{Back pain} + 0.06 * \text{Duration of Morning Stiffness} + 0.11 * \text{Patient Global} + 0.07 * \text{Peripheral Pain/Swelling} + 0.58 * \text{Ln}(\text{CRP}+1)$$

Disease activity states are inactive disease, moderate disease activity, high disease activity, and very high disease activity. The 3 values selected to separate these states were:

- < 1.3 between inactive disease and moderate disease activity,
- < 2.1 between moderate disease activity and high disease activity, and

- 3.5 between high disease activity and very high disease activity.

Selected cutoffs for improvement scores were a change  $\geq 1.1$  unit for “clinically important improvement” and a change  $\geq 2.0$  units for “major improvement” ([Machado 2011](#)).

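### Imputing each ASDAS component in its own model ignores residual correlation between components and understates imputed response at the planned 10–20% rates

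*SAP*

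**What the plan says.** SAP 2.5.3 makes non-responder imputation the main rule for missing ASDAS response and adds: "In an additional analysis, missing data for ASDAS inactive disease response will be imputed using multiple imputation".

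SAP 5.4.1 gives the method. The data set for each run "should only include one component of the composite variable", and the variable list is "var weight_Week16 var1_Week16 var1_week20-var1_week52", run by treatment and TNF-alpha inhibitor status. It continues: "This procedure should be repeated separately for each component of the composite variable". ASDAS and response are then computed from the completed components. No step links the components during imputation. A patient must also have some history to be imputed: "Only dataset rows with a non-missing baseline assessment and at least one non-missing post-baseline assessment will be included".

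SAP 2.11.1 defines the score: "Parameters used for the ASDAS calculation include spinal pain (BASDAI question 2), the patient's global assessment of disease activity", followed by peripheral pain/swelling, duration of morning stiffness and CRP. The weights are 0.12 for back pain, 0.06 for stiffness duration, 0.11 for patient global, 0.07 for peripheral pain and 0.58 for Ln(CRP+1). The response cut-off is given as "< 1.3 between inactive disease and moderate disease activity".

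**The concern.** ASDAS is a sum with positive weights, and its parts can be expected to rise and fall together within a patient. If the missing parts are drawn independently given their own histories, high draws on one item offset low draws on another, and the sum varies too little. At planned response rates of 10% and 20%, the cut-off of 1.3 lies in the lower tail, so a sum that is too narrow crosses it too seldom. SAP 5.4.1 also says that it wants an imputation model that assumes no more about relations in the data than the analysis model does. Zero residual correlation between pain, global assessment, stiffness and CRP is a strong, untested assumption.

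What is at stake is the robustness check. Non-responder imputation credits missing patients with no response. All that multiple imputation adds is the response that it credits to them. If part of that is lost by construction, agreement between the two analyses looks more reassuring than it is. The supportive analysis in SAP 2.5.4 is no substitute, because it changes the form of the interval and not the handling of missing data.

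**Working it through.** **The plan's own figures (SAP 3).** With 97 per arm and rates of 20% and 10%, SE = √(0.20×0.80/97 + 0.10×0.90/97) = 5.08 points, and 1.96 × 5.08 = 9.95 points. Enrolment: 270 × 0.9 × 0.8 = 194.4. Both reproduce.

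**Inputs.** The weights, the cut-off, the variable list and the planned rates come from the SAP. The documents give no component SDs, no correlations between components or visits, and no dropout rate for Treatment Period 2. These are therefore assumed: item SD 2.0–2.5, SD of Ln(CRP+1) 0.6–1.0, correlation among the four patient-reported items 0.4–0.75, and correlation with CRP 0.1–0.3.

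**Closed form.** Let V_J be the variance of ASDAS with the components correlated and V_I the variance with them independent. Let R² be the share of each component's variance explained by its own history. Under separate runs,

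V_imp = R²·V_J + (1 − R²)·V_I, and imputed P(ASDAS < 1.3) = Φ(z_p·√(V_J/V_imp)), where p is the true rate.

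One case in full, with item SD 2.0, Ln(CRP+1) SD 0.6, item correlation 0.6 and CRP correlation 0.2:

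- The four item weights sum to 0.36, and their squares sum to 0.035.
- V_I = 4 × 0.035 + 0.58² × 0.6² = 0.140 + 0.121 = 0.261 (SD 0.51).
- V_J = 4 × [0.035 + 0.6 × (0.36² − 0.035)] + 0.121 + 2 × 0.2 × (0.36 × 2.0) × (0.58 × 0.6) = 0.367 + 0.121 + 0.100 = 0.588 (SD 0.77).
- With R² = 0.5, V_imp = 0.425 and √(0.588/0.425) = 1.177.
- At p = 10%, Φ(−1.282 × 1.177) = 6.6%, a ratio of 0.66. At p = 20%, Φ(−0.842 × 1.177) = 16.1%, a ratio of 0.80.

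Over the assumed ranges, imputed P divided by true P is:

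| Share explained by own history | 10% arm | 20% arm |
|---|---|---|
| 30–70% | 0.41–0.88 | 0.64–0.94 |
| 0% (all correlation lost) | 0.15–0.59 | 0.39–0.76 |

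**Direction for one patient.** In the worked case, with the same correlations in the part not explained by history, the multiplier on z is √(0.588/0.261) = 1.50. A true conditional probability of 10% becomes 2.7% and 20% becomes 10.3%. A probability of 50% is unchanged, and 80% rises to 89.7%.

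**Simulation.** Ten visits by five correlated components were simulated with dropout depending on Week 16 ASDAS and about 16% of an arm imputed (an assumption). The 0–10 limits were not applied. Response among imputed patients was:

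| Arm rate | True | Joint imputation | Separate runs | Separate/joint |
|---|---|---|---|---|
| 10% | 6.2–8.2% | 6.2–8.3% | 2.5–4.8% | 0.32–0.72 |
| 20% | 13.5–17.1% | 13.4–17.1% | 8.8–12.2% | 0.53–0.82 |

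- Whole-arm rates fell by 0.3–0.9 points in the 10% arm and by 0.4–1.3 points in the 20% arm. The difference between arms therefore shrank by about 0.1–0.3 points.
- The share of multiple imputation's contribution that is lost is 1 − 0.82 = 18% to 1 − 0.32 = 68%.

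**Scale limits.** A further run assumed item means 3–4, SD 2, Ln(CRP+1) mean 1.3 and SD 0.6, item correlation 0.3–0.7 and CRP correlation 0.2. With the SAP's limits applied, 5–13% fell to 2–8% (ratios 0.28–0.76), so the limits do not remove the bias. Under the same assumptions, with only hs-CRP missing and no limits applied, the ratio was 0.74–0.92.

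**Check of a remedy.** Imputing ASDAS itself as one series gave 4.8% against a true 4.8% (separate runs 2.6%) in a 10% arm, and 11.0% against 11.1% (separate runs 7.6%) in a 20% arm, again under assumed correlations.

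**The case against.** Several limits on the point stand.

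- **Correlation is not destroyed.** A reader might infer that separate runs remove all association between components. They do not. Each run conditions on that component's own Week 16 and later values, and those histories are themselves correlated across components. Only the residual part is lost.
- **No single factor can be claimed.** A reader might infer that imputed response is roughly halved. One half is one point in a range set by correlations that the documents do not report.
- **The direction is not universal.** The bias reverses for a patient whose history predicts response with probability above 50%.
- **Not every gap involves all five components.** The protocol allows telephone visits, and its Table 6-1 appears to mark BASDAI and patient global for them. Such a visit could leave only hs-CRP missing, where the loss is smaller.
- **The treatment comparison barely moves.** Both arms shift the same way. A fall in one arm's rate should not be set against the planned 10-point difference.
- **The analysis still tests something.** A reader might infer that it cannot probe sensitivity at all. It still credits missing patients with more than the zero given by non-responder imputation. It is attenuated, not empty.

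What does not stand is the suggestion that the matter is too small to correct. Measured against what multiple imputation is there to add, the simulated loss is 18–68%.

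**Conclusion.** The point holds as a moderate flaw in the specification of an additional analysis. The separate runs are explicit in SAP 5.4.1, and their effect on the variance of the sum follows from the ASDAS formula once the components are positively correlated. At the planned 10–20% rates, imputed response is biased low, to about 0.3–0.9 of the correct probability.

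That range rests on assumed SDs, correlations and strength of history, because the documents supply none. The arm-level figures also assume about 16% imputed. The primary non-responder analysis is unaffected, and the treatment difference changes by a few tenths of a point against a planned half-width of 10. The harm is to interpretation: the only alternative missing-data method planned for the primary endpoint leans toward the result that it is meant to check.

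**What to change.** Replace the five separate runs in SAP 5.4.1 with one PROC MI run by treatment, with TNF-alpha inhibitor status as a covariate. Impute two linked longitudinal series:

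- the weighted patient-reported sum (0.12, 0.06, 0.11 and 0.07 times the four items), limited to 0–3.6, since 0.36 × 10 = 3.6;
- log(hs-CRP+1), with a minimum of 0.

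Enter each series only at its planned visits, because hs-CRP may be measured less often. Then compute ASDAS and dichotomise at 1.3. An observed patient-reported sum at a visit then informs a missing hs-CRP at that visit. Alternatively, impute ASDAS itself as one series at the visits where it is planned. That is simpler, but it discards patient-reported values from visits without hs-CRP.

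The model size is manageable. Two series over ten visits (Weeks 16 to 52), plus weight and TNF status, make at most 22 variables for about 97 patients per arm. A full five-component model would need 5 × 10 + 1 = 51 variables. Run by TNF status, it would face about 97 × 0.40 ≈ 39 TNF inadequate responders per arm, if the 40% enrolment cap is reached and carries through to randomization.

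Report the result beside the component-wise version. Label it supplementary, because the SAP's document history dates the current version 08-Jul-2021, after database lock. The cost is a little extra code and one post hoc label; no new data are needed.
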